9.2. Possible Toxicities

Based on the safety experience in the first 70 patients, the most common treatment associated adverse event is injection site pain. Other constitutional adverse events (nausea, vomiting, decreased appetite and anorexia) have also been reported.

Additional theoretical toxicities that could be affected by INT230-6, which may or may not be increased with the combination of immune activating agents, such as hematologic, cardiovascular, hepatic, musculoskeletal, and other systems, and may include the following:

- Allergic reaction/hypersensitivity: Fever, chills, shakes, itching, rash, hyper- or hypotension, and difficulty breathing. It is likely that most injection-related adverse events will occur within the first 24 hours after the injection and may be treated by supportive treatment as indicated.
- Injection procedure: Pain during and after the injection, bleeding, infection, tumor ulceration and edema. The needle utilized for this is the same or smaller size than what is typically used for a biopsy. All attempts at using a single injection point for each tumor are suggested. Additionally, injection volumes of liquid into the tumor should provide some back pressure to help reduce the potential for bleeding. The Quadrafuse device has been used for injection of deep tumors and has a low rate of hemorrhage as a complication.
- Other potential adverse effects of INT230-6: Fatigue, anemia, leukopenia, hyponatremia, other laboratory abnormalities (including increases in gamma-glutamyl transferase (GGT), aspartate aminotransferase (AST) and alanine aminotransferase (ALT), lipase, creatinine), nausea or vomiting, decreased appetite, weight loss, muscle aches, chills, dizziness, and urinary retention.
- Adverse effects associated with IV Cisplatin and Vinblastine are less likely given the dose used in this study: Renal damage, visual disturbances, hearing loss/tinitis, peripheral neuropathy, sensory loss/numbness, tingling, areflexia

and difficulty walking, xerostomia or xerosis, dehydration, dysgeusia, alopecia, thrombocytopenia, other blood abnormalities (low magnesium, calcium, potassium), bleeding, dark urine, chest pain or heart attack, sweating, depression, muscle cramps, pain including headaches.

- Extravasations: There are no reports of simultaneous extravasations of CIS and VBL so guidance on countermeasures does not exist. Also watch closely for any toxicities when given intradermally for skin tumors.

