- Vital sign measurements to include temperature, pulse, O₂ saturation and resting blood pressure as defined in the Time and Events Schedule ([Table 11](#) for every 28 day dosing and [Table 12](#) for every 14 day dosing). Vital signs will be obtained before injection and then 15, 30, 60 post injection. In addition, 180 and 360 minutes post injection vital signs are collected at C1D0.
- Weight;
- Assessment of signs and symptoms;
- Adverse Event Assessment;
- ECG;
- ECOG performance status;
- Serum sample for pharmacokinetics is eliminated in Amendment 6. Clinical laboratory tests (local laboratories; Hematology (using ~5 mL of blood), coagulation

and clinical chemistry laboratories (using ~5 mL of blood) **must be performed and reviewed before dosing**. Labs do not need to be repeated if obtained within 72 hours of starting treatment). This includes a CBC with differential and Chemistry as outlined in Section 12.1.2;

- Any new \geq Grade 3 laboratory abnormality such as liver function test elevations, electrolyte fluctuation, or hematologic deterioration should be assessed for potential risk to continued dosing. In the event of uncertainty, the Sponsor Medical Monitor should be contacted;
- Urinalysis;
- Serum or urine pregnancy test to be performed locally (for all women of childbearing potential; pregnancy test must be negative before study drug administration to continue);
- CT/MRI Brain screening: CT/MRI Brain, only if clinically indicated by the development of new symptoms that suggest new CNS involvement;
- Tumor imaging (CT/MRI or PET/CT chest/abdomen/pelvis) **to be conducted only if imaging has not occurred within previous 29 days**;
- US/CT measurements of injected tumor;
- Response assessment and documentation;
- Cryopreserved peripheral blood mononuclear cells (PBMCs) and serum. **Collection eliminated in Amendment 6.**
- Tumor and blood samples that are available after completion of designated analyses may be used in the future for identification of potential predictive and/or pharmacodynamic markers. These assessments will provide exploratory insights into the immunomodulatory activity of INT230-6.;
- Concomitant medications;
- INT230-6 injections (after all other evaluations for the visit according to the Time and Events ([Table 12](#)) have been completed except for the post injection vital signs);

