- Over 20 subjects have received INT230-6 more than 3 times into both superficial and deep tumors, with more than 10 subjects having had multiple deep tumor injections. The SSC reviewed the subject safety on February 8th, 2019 and authorized initiation of biopsies from both superficial and deep tumors; On Cycle 1 Day 0, an on-study biopsy of an injected tumor is mandatory prior to INT230-6 injection. If possible, a biopsy of one (1) bystander tumor selected and taken by the attending physician; however, if risk is too high to such bystander tumor, then the biopsy should not be taken. The SSC shall review periodically to determine whether subject biopsies can continue to be taken.

12.1.3.2. Cycles/Doses 2 - 5

INT230-6 injections (after all other evaluations for the visit according to the Time and Events Table have been completed except for the post-injection vital signs). During cycles 4 and 5 there

is no scheduled dosing of INT230-6 for patients being dosed every 14 days (E cohort, may apply to combination cohorts, see supplement for specific schedules).

- Physical Exam: A Targeted physical examination will be conducted at all visits;
- Vital sign measurements to include temperature, pulse, O₂ saturation and resting blood pressure. On the day of each injection, vital signs will be obtained before injection and then 15, 30 and 60 minutes post injection;
- Weight;
- ECOG performance status;
- Any new \geq Grade 3 laboratory abnormality such as liver function test elevations, electrolyte fluctuation, or hematologic deterioration should be assessed for potential risk to continued dosing. In the event of uncertainty, the Sponsor Medical Monitor should be contacted.;
- Hematology with differential;
 - Coagulation
- Clinical chemistry; as outlined in Section 12.1.2.
- First tumor imaging (CT/MRI chest/abdomen/pelvis) should be done at 12 weeks +/- 10 days from the date of the first baseline scan (Cycle 1, D0) with repeat scans every 9 weeks +/- 10 days thereafter until end of study or confirmed progression whichever occurs first;
- Urinalysis;
- Serum or urine pregnancy test to be performed locally (for all women of childbearing potential; pregnancy test must be negative before study drug administration to continue);
- Response assessment and documentation;

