Adverse events will be coded using the Medical Dictionary for Regulatory Activities (MedDRA) to categorize a system organ class and a preferred term for each adverse event. The number of subjects who experienced at least 1 adverse event, study drug related adverse event, severe (Grade 3 or above) adverse event, serious adverse event, and the number of subjects withdrawn due to adverse events will be summarized. For each system organ class and preferred term, summaries will be made with respect to the number and proportion of subjects having at least 1 occurrence of an adverse event during the study, using the worst grade reported within a subject. The incidence of adverse events will be presented overall, by system organ class and preferred term, intensity (based on NCI CTCAE Version 4.03), and additional grouping by severity and relationship to study drug. Individual listings of adverse events will be provided.

DLTs and study drug-related Grade >2 adverse events will be listed individually.

Physical Examination

Abnormal PE findings with onset prior to first dose of study drug will be recorded as medical history. Any abnormal or clinically significant findings on or after dosing will be recorded as an adverse event. Clinical significance will be determined by the Principal Investigator at each site.

Individual medical/surgical history will be listed by subject. Individual abnormal or clinically significant PE findings after dosing will be recorded as an adverse event and listed separately with AEs.

Vital Signs

Vital sign measurements and change from baseline will be summarized. Vital signs include weight, systolic blood pressure (SBP), diastolic blood pressure (DBP), body mass index (BMI, derived), heart rate, oxygen saturation, and temperature. Individual vital sign measurements will be listed.

ECGs

ECG data will be read and interpreted locally. Summary statistics of ECG overall interpretation will be displayed. Per subject ECG test results at will be listed.

Abnormal clinically significant ECG findings on or after informed consent will be recorded as an adverse event and displayed with AEs.

Clinical Laboratory Tests

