 - The baseline value for a given parameter is the last non-missing value prior to the first dose. A value is considered to be post-baseline if it is obtained after the first study drug administration.

- Change from baseline is calculated as (post-baseline result – baseline result). Percent change from baseline is calculated as (change from baseline/baseline results * 100). If either the baseline or post-baseline result is missing, the change from baseline and/or percent change from baseline is set to missing as well.
- Data from study centers will be pooled for all analyses
- Study Day is defined as calendar date – date of first treatment + 1 if the calendar date is on or after the date of first treatment, and calendar date – date of first treatment if the calendar date is before the date of first treatment
- Measurements from unscheduled visits will be included in listings, but not summary tables
- Missing data conventions for individual endpoints are described in detail below for the endpoints
- Listings will be provided of all data collected in the electronic Case Report Form (eCRF)
- Wherever possible, data will be decimal aligned
- For continuous variables, use the following conventions for significant digits: mean (xx.x), median (xx.x), standard deviation (xx.xx), minimum (xx.x) and maximum (xx.x). If data results are less than 1, format decimal points to one more place than the measured value for all summary variables except format to two more places for standard deviations
- Version 25.1 of MedDRA will be used for this study.
- WHODRUG Enhanced Sep-2022 B3 will be used for this study.

The accompanying table, listing, figures (TLF) document to this SAP provides the expected layout and titles of the tables, figures, and listings. Any changes to format, layout, titles, numbering, or any other minor deviation will not necessitate a revision to the SAP nor will it be considered a deviation from planned analyses. Only true differences in the analysis methods or data handling will necessitate such documentation. Please refer to the SAP appendix for additional programming notes.

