10.3. Vital Signs

Vital sign measurements and change from baseline will be summarized by cohort, tumor type and study visit using descriptive statistics. Vital signs include weight, systolic blood pressure (SBP), diastolic blood pressure (DBP), body mass index (BMI, derived), heart rate, oxygen saturation, and temperature. Individual vital sign measurements will be listed.

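### From the second injection on, the planned change in timed post-injection vital signs adds drift since the first dose to the acute effect; a same-session reference is a cheap improvement

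*Protocol*

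**What the plan says.** **Collection.** Protocol 12.1.3.1, for Cycle 1 Day 0: "Vital signs will be obtained before injection and then 15, 30, 60 post injection". Readings at 180 and 360 minutes are added on that day. Protocol 12.1.3.2, for later doses: "On the day of each injection, vital signs will be obtained before injection and then 15, 30 and 60 minutes post injection". Footnote 4 to the schedules of events repeats this for every injection day, and the maintenance column of Table 12 carries the same footnote.

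**Analysis.** SAP 10.3: "Vital sign measurements and change from baseline will be summarized by cohort, tumor type and study visit using descriptive statistics". Protocol 14.3.5 says only "Vital sign measurements and change from baseline will be summarized" and leaves baseline undefined.

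**Reference.** SAP 7.1 sets baseline as "The baseline value for a given parameter is the last non-missing value prior to the first dose" and adds: "A value is considered to be post-baseline if it is obtained after the first study drug administration". A pre-injection reading at dose 2 or later is therefore a post-baseline value and never a reference. No section makes an exception for vital signs. The only re-baselining in the SAP concerns injected tumor response in retreated subjects who change cohort (Appendix 1, item 3).

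**Time points.** SAP 7.1 also asks for a summary at each defined time point. SAP 10.3 itself names only the study visit.

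**The concern.** The design pairs a pre-injection reading with timed readings after it, and the natural use of that pair is the within-session change. Protocol 9.2 lists raised or lowered blood pressure among possible hypersensitivity signs and says: "It is likely that most injection-related adverse events will occur within the first 24 hours after the injection". The planned table does not use the pair after dose 1.

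Two features of this trial make the later sessions worth reading cleanly. In the escalation cohorts the permitted total volume rises over the course: from 5 to 15 mL in A1 (Table 4), 30 to 120 mL in EC (Table 7a) and 100 to 220 mL in EC2 (Table 7b). The largest permitted exposures therefore fall where the change is mixed with drift. In addition, Table 9 mentions prophylactic antihistamines, low-dose corticosteroids and pain medication before later doses, any of which could shift a later pre-injection reading.

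A hypothetical pair of subjects shows the effect. One has drifted up 20 mmHg since the first dose and falls 25 mmHg after dose 5; the table records 20 − 25 = −5. The other has drifted down 20 mmHg and does not react; the table records −20. The non-reactor looks worse.

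**Working it through.** The plan states no figure for this point, so there is nothing to reproduce. The check uses the definitions, the dosing calendar and an assumed range for precision.

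1. **Decomposition.** Let B be the pre-first-dose value, Y(0) the pre-injection reading of a later session and Y(t) the reading t minutes after it. The planned change is

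   Y(t) − B = [Y(t) − Y(0)] + [Y(0) − B] = acute change + drift.

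   At the first injection Y(0) = B, provided that day's pre-injection reading was recorded, so the drift term is zero. It is generally not zero afterwards.

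2. **Age of the reference** (nominal dosing days, Protocol 12.1.3.1; maintenance interval and two-year limit from the Synopsis).
   - E cohorts, Days 14, 28, 42, 56: 2, 4, 6, 8 weeks. SAP Table 3 gives DEC, DEC2 and FEC the same two-weekly interval.
   - A1/B1, Days 28, 56, 84, 112: 4, 8, 12, 16 weeks.
   - Maintenance, assuming a first session 9 weeks after Day 56 and one every 9 weeks after that: from Day 56 + 63 = 119 to Day 56 + 10 × 63 = 686. Dividing by 30.4375 gives 3.9 to 22.5 months, over 10 sessions.
   - With the same-session reference, the lag at these sessions is 15 to 60 minutes.

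3. **What the planned tables still allow.** The pre-injection reading has its own change from B. For subjects with both readings,

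   mean[Y(15) − B] − mean[Y(0) − B] = mean[Y(15) − Y(0)],

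   because B cancels. The spread does not follow: Var[Y(15) − Y(0)] = Var[Y(15)] + Var[Y(0)] − 2 Cov[Y(15), Y(0)], and the covariance is not tabulated. Per-session extremes cannot be read from separate summaries at each time either.

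4. **Precision (assumed inputs).** With equal SDs, a difference of two readings with correlation r has SD × √(2(1 − r)). Take within-session correlation 0.7 to 0.9 and between-visit correlation 0.4 to 0.6. The ratio of the planned SD to the same-session SD is then
   - smallest: √((1 − 0.6)/(1 − 0.7)) = 1.15;
   - largest: √((1 − 0.4)/(1 − 0.9)) = 2.45.

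   A variance-component version, with assumed visit-to-visit SDs of 8 to 12 mmHg and within-session SDs of 5 to 7 mmHg, gives √(2(64 + 25)) = 13.3 against √2 × 5 = 7.1, and √(2(144 + 49)) = 19.6 against √2 × 7 = 9.9. That is a little under two.

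**The case against.** A single pre-first-dose baseline is a consistent convention for descriptive safety tables, and much of the information survives it. SAP 7.1 calls for each defined time point to be summarized, so a reader should not infer from SAP 10.3 that the 15-, 30- and 60-minute readings are pooled within a visit. The group mean acute change can be recovered by subtraction (step 3), so drift and reaction are not inseparable. Every individual value is listed, so both hypothetical subjects could be read correctly there. The table shells are a separate document that was not available and may already show pre- and post-injection rows together.

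Acute reactions are also captured mainly as adverse events. These are graded, with relationship to drug and to dosing procedure recorded separately (Protocol 13.1), and significant worsening on any safety assessment is reported as one (Protocol 13.6). A reader might infer that reactions would go undetected or that the primary safety result is compromised. The documents do not support that: the primary endpoint is related adverse events of grade 3 or higher, which does not use this table.

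All of this stands. It leaves one gap: no planned summary gives the distribution or the extremes of the within-session change, and the one change that is tabulated mixes two quantities.

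**Conclusion.** The point holds as a low-cost improvement to a supporting safety display. From the second injection on, the planned change at 15, 30 and 60 minutes equals the acute change plus drift. This follows from the SAP's definitions and needs no assumption about the data. The age of the reference rests on nominal dosing days; the maintenance figure also assumes uninterrupted nine-weekly sessions up to two years. The size and direction of the drift are unknown. The first injection is unaffected if its pre-injection reading is recorded.

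A claim that the planned analysis is about twice as noisy would go too far. The documents give no SD or correlation for vital signs, the assumed ranges run from 1.15 to 2.45, and no test or decision rule depends on this SD. Nor does Protocol 14.3.5 need correcting: its sentence fits either reference, and the issue lies in SAP 7.1 read with 10.3.

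**What to change.** In SAP 10.3, with a matching exception in 7.1:

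- Define the reference for timed post-injection vital signs as the pre-injection reading of the same session.
- Summarize change at 15, 30 and 60 minutes (plus 180 and 360 minutes at Cycle 1 Day 0) by dose number and treatment group.
- Add the largest fall and largest rise per session.
- Keep change from the pre-first-dose value for the pre-injection readings, where it shows longer-term trend.

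Protocol 14.3.5 can stay as it is. The cost is one derived variable and one extra table, from data the protocol already collects. SAP section 2 requires the plan to be final before database lock; if the table is added later, label it post hoc.

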14.4. Efficacy

14.4.1. Pharmacokinetic Parameters

The release kinetics of each analyte is not expected to be uniform across subjects. Sponsor shall assess the blood concentrations of the three analytes for each subject at the first cycle. Sponsor shall correlate the systemic measurement [maximum plasma drug concentration (Cmax), area under the curve (AUC)] of the 3 analytes to measured markers of systemic toxicity [in particular renal and blood – the known toxicities of the two active agents; cisplatin (CIS) & vinblastine (VBL)]. Human plasma will be analyzed for the concentration of VBL and 8-((2-hydroxybenzoyl)amino)octanoate (sodium salt form) (SHAO) using validated LC/MS/MS methods, and for cisplatin using a validated ICP-MS method. For pharmacokinetic profiling platinum drugs, total platinum levels in subject plasma or urine are routinely determined by spectroscopy methods as a surrogate. Thus, an ICP-MS method is developed for this study to measure total platinum in human samples as a surrogate for cisplatin.

In addition, scatter plots of Cmax and AUCTAU versus INT230-6 dose volume will be provided for the first cycle. Dose proportionality per subject normalized to tumor volume will be assessed, by estimating the slope of linear regression of SHAO/CIS/VIN log(Cmax) on log(dose) and of log(AUCTAU) on log(dose) based on a power model. Point estimates and 90% confidence intervals for the dose proportionality parameter (slope of the linear regression) will be calculated for Cmax and AUCTAU. Summary statistics for trough [minimum plasma drug concentration Cmin] concentrations will be tabulated by dose and study cycle. Plots of Cmin vs. cycle will be assessed for cohorts by combining A1, B1 versus E Cohorts and grouping subjects by similar dose volumes of INT230-6. Pharmacokinetic concentrations from sparse samples will be listed, and may be used in combination with other studies for exposure-response or population pharmacokinetic modeling, which will be part of a separate report.

Administrative interim analyses of pharmacokinetic may be provided at various times during the study in order to support program decisions or publications. PK sampling has been eliminated in Amendment 6.

14.4.2. Exploratory Biomarkers (Immune Function and others)

The pharmacodynamic effects based on the immunomodulatory activity of INT230-6 on selected immune cell populations (for example, T-cell repertoire and their changes (or percent changes) on flow cytometry) and soluble factors in blood (cytokines), exploratory immune function markers including flow cytometry markers, humoral and cellular immune responses to tumor antigens (quantitative immunoglobulins, quantitative inflammatory infiltrates, when available) and a panel of recall non-tumor antigens will be assessed by summary statistics for outcomes from these markers and their changes (or percent changes) from baseline tabulated. In addition, the time course of biomarker outcomes will be conveyed graphically, by summary plots (i.e., box plots) or individual subject plots over time. Possible associations between changes in biomarker measures of interest and pharmacokinetic exposure will be explored. Possible associations of various biomarkers measures (baseline value or change from baseline) with clinical outcome (e.g., tumor response) may will be explored based on data availability, using response-evaluable subjects, to assess predictive markers in tumors. Methods such as, but not limited to, logistic regression may be used to explore such associations. Measures from markers based on optional samples, e.g., tumor-based markers may be similarly presented, depending on data availability.

Potential associations of various biomarker measures (baseline value or change from baseline) with clinical outcome (e.g., tumor response or disease control) will be explored e.g., for expression levels of PD-L1 protein measured by immunohistochemistry techniques in tumor sections at baseline may be explored based on data availability, using response-evaluable subjects, to explore assess potential predictive effects of these

Protocol IT-01 Version Amendment 6

markers. Methods such as, but not limited to, logistic regression may be used to further assess such associations.

Measures from markers based on optional samples, e.g., tumor-based markers may be similarly presented, depending on data availability.

Administrative interim analyses of biomarker data may be provided at various times during the study (e.g., for the initial and the additional study cohorts) in order to support program decisions or publication. Blood biomarker assessments have been eliminated in Amendment 6.

